# 12.1. Adverse Events / Adverse Drug Reactions

An adverse event (AE) is any untoward medical condition that occurs in a patient while participating in this clinical study. Adverse events will be coded according to the Medical Dictionary for Regulatory Activities (MedDRA 25.0 or later) terminology and the severity of the toxicities will be graded according to the National Cancer Institute (NCI) Common Toxicity Criteria for Adverse Events (CTCAE), v4.03, where applicable. An adverse drug reaction (ADR) means any AE caused by a drug or biologic.

This document is confidential.

SAP text Version: SAP text 3.0 6-Dec-2023

Controlled Document ID: 3903A.02, Effective Date 31-Aug-2020

A Clinical Adjudication Committee (CAC) will review selected treatment emergent neurological adverse events that are known to occur as the result of dopamine receptor antagonists (see Appendix 16.5). The details of the CAC procedures and adjudication process will be reported in a CAC charter.

Treatment-Emergent Adverse Events (TEAEs) are those adverse events/adverse drug reactions that are recorded during or following the initiation of study treatment administration, and do not necessarily have a causal relationship to the use of the study medication. Treatment-Emergent Adverse Events (simply referred to as adverse events in summary tables) will be summarized.

The following adverse event summary tables will be summarized by treatment group:

- An overall summary with the number and percentage of patients reporting AEs, serious AEs
  (SAEs), maximum severity AEs, treatment-related AEs, treatment related SAEs, AEs leading to
  study treatment discontinuation and AEs with outcome of deaths.
- 2) AEs overall and by system organ class and preferred term.

In this summary, a patient is counted once at the system organ class and once at each preferred term within the system organ class.

- AEs overall and by system organ class, preferred term and initial daily dose level.
- 4) AEs overall and by system organ class, preferred term and region.
- 5) AEs overall and by system organ class, preferred term and weight band.
- 6) AEs overall and by system organ class, preferred term and time within the titration phase of open-label stabilization period. In all summaries by time the time windows are based on time since fist dose of ecopipam and will be as follows: 1-7, 8-14, 15-21, 22-28, 29-56, 57-84, 85-91, 92-98, 99-105, 106-112, 113-126, 127-140, 141-154, 155-168, 169-175, 176-184.
- 7) AEs overall and by system organ class, preferred term and time within open-label stabilization period.
- 8) AEs overall and by system organ class, preferred term and time within the double-blind randomized withdrawal period.
- 9) AEs overall and by system organ class, preferred term and time within the safety follow up.
- 10) AEs overall and by system organ class, preferred term and maximum severity.

In this summary, a patient is counted once at the highest severity for which the event occurred in the system organ class and the highest severity for each unique preferred term within that system organ class. Therefore, patients may only contribute once to each preferred term and once to each system organ class.

11) Study-treatment-related AEs overall and by system organ class and preferred term.

All those AEs with relationship to treatment marked as "Possibly Related" or "Probably Related" or missing will be reported in the table.

- 12) Study-treatment related AEs by system organ class, preferred term and maximum severity
- 13) AEs leading to study treatment termination by system organ class and preferred term.
- 14) AEs leading to study treatment termination by system organ class, preferred term and maximum severity.
- 15) AEs by maximum severity, maximum relatedness and milestones (Up-titration, Open-label maintenance, double-blind R/WD (Weeks 13-16), double-blind R/WD (Weeks 17-24) and Down-titration).

A Serious Adverse Event (SAE) is an AE which falls into one or more of the following categories:

- Results in death.
- · It is immediately life-threatening.
- It requires in-subject hospitalization or prolongation of existing hospitalization.
- It results in persistent or significant disability or incapacity.
- Results in a congenital abnormality or birth defect.
- It is an important medical event that may jeopardize the subject or may require medical intervention to prevent one of the outcomes listed above.

Serious adverse events will be summarized by treatment group and combined over both treatment groups. A summary by age group (Children (≥ 6 and < 12 years of age), Adolescents (≥ 12 and < 18 years of age), and Adults (≥ 18 years of age)) will also be provided.

16) SAEs overall and by system organ class and preferred term.

In this summary, a patient is counted once at the system organ class and once at each preferred term within the system organ class.

- 17) Treatment related SAEs overall and by system organ class and preferred term.
- 18) Adverse events of special interest (AESI) summary tables will include weight gain, extrapyramidal reactions (AESIs associated with Dopamine blockade/dopamine antagonists) and suicidal ideations and behavior. More details are in section 16.5. These summaries will include severity, relatedness, and timing with respect to first dose of ecopipam.
- 19) Most common AEs (>= 5%) experienced during treatment period will be summarized by preferred term.

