During the R/WD period, subjects will return to the clinic every week for the first 4 weeks and every 2 weeks thereafter (Weeks 13, 14, 15, 16, 18, 20, 22 and 24) and efficacy and safety assessments will be conducted at each of these visits.

Any subject meeting Relapse criteria, defined as loss of $\geq 50\%$ of the improvement experienced on the YGTSS-TTS from Baseline (Day 1) to the last visit of the open-label Stabilization period (Week 12), or initiation of additional medications to treat symptoms of TD, or requirement of hospitalization for worsening symptoms of TD will be withdrawn from blinded study medication (ecopipam or placebo).

Non-responders to ecopipam during the open-label Stabilization period at either Week 8 or Week 12, or Responders randomized to ecopipam who complete the R/WD period, or who meet

Relapse criteria during the R/WD period, or who discontinue the study prematurely for any reason will be tapered off ecopipam in decrements of 22.4 mg/day (25 mg/day ecopipam HCl) and will complete the Week 24/Relapse/ET visit. Subjects assigned to placebo will receive placebo taper down medication to preserve the blind.

Follow Up visits will be conducted in the clinic 7 and 14 days after the last dose of study medication followed by a telephone call 30 days after the last dose of study medication to determine any adverse events, with the exception of subjects who roll into the open-label extension study EBS-101-TD-391within 30 days of their last study drug.

Subjects who experience Relapse may be treated for their TD with medications recommended by the PI or referred back to their primary physician for treatment after completing Day 7 and 14 follow-up visits.

[figure not shown]
Responders to ecopipam who complete the R/WD period and who complete the Week 24/Relapse/ET visit and the Day 7 and 14 follow-up visits are eligible to enter the long-term open-label study EBS-101-TD-391. Subjects who meet the criteria for Relapse and complete the Week 24/Relapse/ET visit and the Day 7 and 14 follow-up visits will have the opportunity to enter the long-term open-label study..

In anticipation of reaching the target number of Relapse events, randomization into the double-blind R/WD period may be closed, at which time subjects in the open-label Stabilization period may continue in the study until the Week 12 visit Upon completion of the Week 12 visit, subjects will have the opportunity to enter the long-term open-label study, EBS-101-TD-391.

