| | Screening Period ^a | Titrati | on Phase | W | Maintenance Phase Weeks 4 to 12 (Day 29 up to 84) | | | Double-Blind Randomized Withdrawal Period Weeks 12 to 24 (Days 85 to 169) | | | | | | | Safety Follow-Up (Days 170-199) | | |
| Visit/TC Study Day | Screening VISIT 1 Day -28 to -1 | Baseline VISIT 2 Day 1 | W 2 f Day 15 Telephone call only (±3d) | W4 / VISIT 3/ Day 29 (±3d) | W8 / VISIT 4 / Day 57 (±3d) | W 12 VISIT 5 Day 85 (±3d) | W13 / VISIT 6 / Day 92 (±3d) | W14 / VISIT 7 / Day 99 (±3d) | W15 / VISIT 8 / Day 106 (±3d) | W16 / VISIT 9 / Day 113 (±3d) | W18 / VISIT 10 / Day 127 (±3d) | W20 / VISIT 11 / Day 141 (±3d) | W22 / VISIT 12/ Day 155 (±3d) | W 24 VISIT 13 Day 169 or Relapse or ET (±3d) | 7 Day F/U VISIT 14 (±3d) | 14 Day F/U VISIT 15 (±3d) | 30 Day F/U ^f Telephone call only (±3d) |
| Dispense Study Drug | | X | | X^d | X | X | | | | X | | X | | X | | | |
| Collect Unused Study Drug/Assess Drug Compliance | | | | X | X | X | X | X | х | x | X | X | X | X | X | | |

Abbreviations: ADHD = attention-deficit hyperactivity disorder; AE = adverse event; BP = blood pressure; DSM-5-TR = Diagnostic and Statistical Manual of Mental Disorders, Fifth Edition; ECG = electrocardiogram; F/U = follow up; HR = heart rate; PK = pharmacokinetic(s); TD = Tourette's Disorder

Neurological exam should be part of the physical exam. Physical exam t Week 4 visit will include assessment for serotonin syndrome. If serotonin syndrome symptoms are present, local laboratory assessment should be performed.

Confidential

^a Informed consent must be obtained prior to any screening procedures. All screening procedures are to occur after confirmation of appropriate timeframe since discontinuation of applicable medications. Rescreening is allowed after approval by the Medical Advisor.

^b Vital signs will include pulse, BP (done 5 minutes after being supine) height and weight.

^c Subjects should be in a fasting state (8 hours) for laboratory t sts. Fas ing at the Screening visit is optional. HbA1c will be measured only at Baseline, Week 12, and Week 24 (completed subjects only).

d At Week 4, ecopipam should be administered after the pre-dose blood draw. PK samples will be collected at 1) pre-dose; 2), post-dose between 0.5 and 1.5 hours; and 3) post-dose between 2 and 4 hours. Week 12 PK assessment only to be performed if Week 8 assessment is missed.

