12.2.1.1. Adverse Event (AE)

An AE is the development of an undesirable medical condition or the deterioration of a preexisting medical condition including worsening of TD following or during exposure to a pharmaceutical product, whether or not considered casually related to the product. In clinical

| Emalex Biosciences, Inc. | |
|--------------------------|--|
| Ecopipam | |

Protocol EBS-101-TD-301 Version 9.0, 05 March 2024

studies, an AE can include an undesirable medical condition occurring at any time, including baseline or washout periods, even if no study treatment has been administered.

All AEs that occur after any subject has been screened, enrolled, before treatment, during treatment, or within 30 days following the cessation of treatment, whether they are related to the study or not, must be recorded on forms provided by Sponsor or its representatives.

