# 16.5. Adverse events of special interest (AESI)

Potential Adverse Events associated with dopamine antagonists

Symptomatic	Psychiatric	Somatic	Neurologic
1. Lethargy / Somnolence / Fatigue / Sedation 2. Dizziness / Lightheadedness / Vertigo 3. sleep disorder 4. Anxiety (Including major anxiety disorder) 5. Nausea / vomiting 6. Diarrhea 7. Sialorrhea 8. Constipation 9. Blurred vision	1. Suicidality 2. Depression (Major and Minor) 3. Psychosis 4. Obsessive / Compulsive behavior	1. Weight gain 2. Orthostatic hypotension 3. Temperature deregulation 4. Metabolic syndrome. 5. Elevated Glucose / HgA1c 6. Increased Total Cholesterol, increased LDL, decreased HDL, increased triglycerides 10. Leukopenia / neutropenia 11. QTc prolongation 12. Arrhythmias (supraventricular and ventricular) 13. Brady / Tachycardia 14. Elevated prolactin 15. Menstrual irregularities 16. Myocarditis / cardiomyopathy	1. Seizures 2. Syncope 3. Dystonia / dynamic dystonia 4. Akathisia 5 Rigidity 3. Bradykinesia 4. Tremor 5. Postural instability 6. Tardive dyskinesia 7. Tardive dyskinesia a/w withdrawal 8. Neuroleptic malignant syndrome 9. Oculogyric crisis
		17. Pancreatitis 18. Cholecystitis	

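### SAP table 9 times follow-up adverse events from the first ecopipam dose and stops at Day 184, so half of a completer's nominal follow-up has no window and onset after stopping cannot be read

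*SAP*

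**What the plan says.** SAP 12.1 introduces the time windows under table 6 and applies them to every by-time table: "In all summaries by time the time windows are based on time since fist dose of ecopipam and will be as follows" (the misspelling is the SAP's). Sixteen windows follow, ending "155-168, 169-175, 176-184". None is open-ended. Tables 6, 7 and 8 cover titration, the open-label period and the randomized withdrawal period. Table 9 is "AEs overall and by system organ class, preferred term and time within the safety follow up".

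The AESI summaries (table 18) use the same origin: "These summaries will include severity, relatedness, and timing with respect to first dose of ecopipam". The event list in SAP 16.5 includes "Tardive dyskinesia a/w withdrawal".

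The collection rules use a different origin. Protocol 12.2.1.1 requires recording of events up to and "within 30 days following the cessation of treatment". Protocol 7.1 states: "Follow Up visits will be conducted in the clinic 7 and 14 days after the last dose of study medication", with a telephone call at 30 days. The schedules (Protocol Table 3, SAP 16.1) label safety follow-up as Days 170-199 and show study drug dispensed at Week 24. Protocol 7.1 and 10.5 require a taper for non-responders, relapsers, early discontinuations and ecopipam completers.

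SAP 8.2 defines separate taper-down (TDAE) and off-study-drug (ODAE) categories. The milestones in SAP Section 12 and table 15 end at down-titration and list no off-drug category.

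**The concern.** Table 9 is the only by-time table listed for the period after study drug. It should answer two questions: what happens over the whole of follow-up, and how soon after stopping events begin. Its windows end before the nominal follow-up does. Its clock runs from first dose, whereas subjects stop at anything from Week 8 to Week 24, so a given study day does not correspond to a given time off drug.

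This matters because the design withdraws drug on purpose, the protocol has all subjects monitored for withdrawal, abuse and dependence, and the AESI list names a withdrawal-associated event. Clustering shortly after the last dose would be spread over many rows of table 9. The AESI timing, also counted from first dose, would not show it either.

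**Working it through.** **Inputs.** Last window ends at Day 184 (SAP 12.1). Week 24 visit is Day 169, Week 8 is Day 57, Week 12 is Day 85, Week 14 is Day 99 (Protocol Table 3). Follow-up lasts 30 days after last dose (Protocol 7.1, 12.2.1.1). Taper decrements are 22.4 mg/day, with the time per step not stated (Protocol 10.5). Maintenance doses run from 33.6 to 179.2 mg by weight band (Protocol Table 5). First dose is taken as Day 1.

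**Reproducing the schedule.** 169 + 30 = 199, so Days 170-199 assumes a last dose on Day 169. The sixteen windows are contiguous from Day 1 to Day 184.

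**Completer, last dose on Day 169.** Days with a window: 184 − 169 = 15. Days without: 199 − 184 = 15, half of the 30. In general, for a last dose on Day L from 154 to 184, the uncovered days are (L + 30) − 184 = L − 154. The ±3-day allowance on the Week 24 visit moves the 15 to between 12 and 18.

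**Effect of a taper after Day 169.** Decrements are dose/22.4, rounded up; reduced non-zero levels are one fewer. Both step lengths below are assumptions, shown only to give a range. Uncovered days are L − 154, capped at 30.

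| Maintenance dose (mg) | Decrements | Reduced levels | 1-day steps: last dose / 14-day visit / uncovered days | 7-day steps: last dose / 30th day / uncovered days |
|---|---|---|---|---|
| 33.6 | 2 | 1 | 170 / 184 / 16 | 176 / 206 / 22 |
| 44.8 | 2 | 1 | 170 / 184 / 16 | 176 / 206 / 22 |
| 67.2 | 3 | 2 | 171 / 185 / 17 | 183 / 213 / 29 |
| 89.6 | 4 | 3 | 172 / 186 / 18 | 190 / 220 / 30 |
| 134.4 | 6 | 5 | 174 / 188 / 20 | 204 / 234 / 30 |
| 179.2 | 8 | 7 | 176 / 190 / 22 | 218 / 248 / 30 |

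Even with one-day steps, the nominal 14-day visit falls after Day 184 in four of the six weight bands.

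**Different stopping times on the first-dose clock** (last dose taken at the stopping visit; a taper would move each later):

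| Subject | Last dose | 30 days after it | Table 9 windows |
|---|---|---|---|
| Week 8 non-responder | Day 57 | 58-87 | 57-84, 85-91 |
| Week 12 non-responder | Day 85 | 86-115 | 85-91 to 113-126 |
| Week 14 relapse | Day 99 | 100-129 | 99-105 to 127-140 |
| Week 24 completer | Day 169 | 170-199 | 169-175, 176-184, then none |

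Row 85-91 therefore holds the Week 8 non-responder at 28-30 days off drug (85 − 57 to 87 − 57) beside the Week 12 non-responder at 1-6 days (86 − 85 to 91 − 85). Conversely, the first seven days off drug for these four subjects are Days 58-64, 86-92, 100-106 and 170-176, which occupy seven different rows.

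**How many stop early.** With the planned 50% response rate (Protocol 7.2), about 98 of 196 children and adolescents are not randomized and stop by about Week 12. Adding all 49 planned relapses gives (98 + 49)/196 = 75%. That is an upper bound on subjects: relapses found at Week 24 should be subtracted, and it does not count events.

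**The case against.** A reader might infer that events after Day 184 drop out of the safety analysis. They do not. TEAEs are defined in SAP 8.2 and Section 12 with a start and no end date, so late events count in the overall, SOC and preferred-term, severity, relatedness and SAE tables and appear in the listings. Table 9 also reports events overall as well as by time. What is missing is a time window.

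A reader might also infer that early stoppers' off-drug events are reported as on-treatment. The day labels coincide with treatment-period days for other subjects, but tables 7 and 8 are restricted to the open-label and randomized withdrawal periods, and table 9 is separate.

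Nor is it right that the plan cannot show events after withdrawal. Placebo subjects begin the blinded taper at randomization, nominally Day 85. The windows become weekly there (85-91 to 106-112), and table 8 displays them against concurrent ecopipam subjects. For that arm the first-dose clock is close to a time-since-withdrawal clock, so re-anchoring placebo subjects in table 9 is unnecessary. Down-titration also has its own milestone, starting after Week 24 or early termination.

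The tail may be thin. Without a taper, the 7- and 14-day visits fall on about Days 176 and 183, inside the last window, and subjects who enter the extension within 30 days skip the telephone call. That limits the number of events affected. It does not give late events a window, and the 14-day visit, which is required before extension entry, moves past Day 184 with quite short tapers.

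The 75% figure and the Day 218 and 248 results are weak support. The first is an upper bound on subjects. On the planning rates about 32 relapses (65% of 49) would be on placebo, whose post-relapse taper kit is placebo. The second pair combines the heaviest weight band with an assumed weekly step.

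**Conclusion.** The concern holds as a defect of table 9 and of the AESI timing. On the plan's own nominal schedule, 15 of a completer's 30 follow-up days have no window. This assumes a last dose on Day 169. Any taper after Week 24 increases the shortfall, by 1 to 7 days across weight bands if each step lasts one day, and by more with longer steps; the interval is not stated. For subjects who stop earlier, about half of the children and adolescents on the planned response rate alone, the first-dose labels mix different times off drug, so table 9 cannot show onset relative to stopping.

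The documents do not support a claim that these events are lost, that they are counted as on-treatment, or that the placebo arm's blinded withdrawal goes unexamined. Overall adverse-event counts and efficacy are unaffected. The change is still worth making, because a stated rule leaves part of its own follow-up period without a window in the table meant to describe it.

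**What to change.** In SAP 12.1:

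- Keep the first-dose windows for tables 6-8.
- Time table 9 from the last dose of study drug, for example Days 1-7, 8-14, 15-30 and >30, with the last window open-ended so that every collected event has a place. Show it by treatment group, so that ecopipam and placebo subjects can be told apart.
- In table 18, add time since last dose for AESIs with onset after stopping, beside the existing time from first dose.
- Carry the ODAE category of SAP 8.2 into the Section 12 milestones and table 15, separate from down-titration.
- State how an unknown last-dose date is handled. The exposure rule in SAP 8.2 substitutes the last clinic visit, which could be a follow-up visit.

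The cost is SAP wording and programming. Onset dates are already recorded (Protocol 12.4), and last-dose dates already enter the exposure derivation. No new data, visits or protocol procedures are needed.

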#### 12.2. Laboratory Evaluations

Blood samples for hematology, chemistry, prolactin and urine samples for urinalysis are to be collected at screening, Baseline, Weeks 12 and 18, Completion [Week 24] or Relapse/Early Termination and 7 day and 14 day Follow Up visits. All results will be provided using International System of Units (SI). HbA1c will be measured at the baseline, week 12 and week 24 completion or early termination visits.

Descriptive statistics for hematology, chemistry, prolactin and HbA1c will be provided for each test parameter and for change from baseline treatment by visit and for each treatment group. Shift tables (i.e., low-normal-high at Baseline versus low-normal-high at each post-baseline visit in a 3-by-3 contingency table) will be provided for hematology, chemistry, prolactin, HbA1c and urine to assess changes from Baseline in laboratory values by visit for each treatment group. Shift (0.5% change) from baseline will be summarized for HbA1c by visit for each treatment group.

Separate listings will be provided for all laboratory evaluations (hematology, chemistry, prolactin, HbA1c and urinalysis.

# 12.3. Vital Signs

Vital sign measurements including blood pressure (after being supine for 5 minutes), pulse, height (children and adolescents only) and weight at each scheduled visit (Screening, Baseline, Weeks 4, 8, 12, 13, 14, 15, 16, 18, 20, 22 and 24 and the 7- and 14-day Follow Up visits) will be summarized with descriptive statistics at each scheduled time point by treatment group.

Changes from baseline for blood pressure and weight will be summarized with descriptive statistics at each scheduled time point by treatment group. Weight will be displayed in kilograms; height will be displayed in centimeters. Shift (0.5 change ranging from <-3 to >3) from baseline will be summarized for weight z-score, height z-score and bmi-z score by visit for each treatment group. Shift (increase or decrease at least 7% change) from baseline will be summarized for weight by visit for each treatment group.

All vital signs data will be presented in a listing.

#### 12.4. ECG

The following ECG data will be collected at the Screening, Baseline, Weeks 4, 12, 18, and 24 and at the 7-and 14-day Follow Up visits:

- PR interval (msec)
- QRS interval (msec)
- QT interval
- QTc interval (msec)
- Overall ECG result (Normal; Abnormal)

An ECG is optional at unscheduled visits, per the investigator's discretion. All ECGs are monitored, interpreted, reported, and analyzed by a core central facility.

All findings will be presented in the ECG listings.

ECG analysis will consist of:

This document is confidential.

SAP text Version: SAP text 3.0 6-Dec-2023

Controlled Document ID: 3903A.02, Effective Date 31-Aug-2020

- Change from baseline for HR, PR, QRS, and QTcF for each treatment group. (QT and QTcB data will be in listings)
- Shift from baseline in overall ECG result.
- Treatment-emergent morphology findings will be listed.
- Categorical outlier analysis for HR, PR, QRS and QTcF by treatment group.
   The following categorical outliers will be summarized:

